In conducting this phase 1 study, we will utilize the multidisciplinary collaboration of an experienced group of scientists, surgeons and physical therapists in a unique environment at the University of Pittsburgh and the USAISR (United States Army Institute of Surgical Research) at Brooke Army Medical Center (BAMC) San Antonio, Texas. The main outcome measures will be to (a) quantify the length and volume of fibrosis in the injured hamstring muscle, based on a baseline 3 Tesla MRI and a subsequent follow-up MRI examination 6 months post-injury and (b) prospectively follow the subjects to evaluate the amount of scarring and time to return to prior activity. Safety and tolerability will be assessed by monitoring adverse events, symptoms (dizziness, new fatigue, peripheral edema or urinary symptoms), hypotension, and laboratory measures of liver and renal function, hemoglobin and hematocrit counts and serum potassium and uric acid levels.

A 1999 study in the United Kingdom^67 examined the safety of losartan potassium post-marketing in over 14,000 patients. The results of this study indicate losartan potassium, like other angiotensin II receptor antagonists (ARBs), does not present any significant adverse events. The most commonly cited specific adverse events include dizziness, headache, malaise, nausea, lassitude, cough, diarrhea, dyspnea and impotence. A literature review conducted by Sica *et al.* found other adverse events being decreases in hemoglobin and hematocrit counts, dysgeusia and ageusia, migraines and acute psychosis, hepatic abnormalities, angioedema, increase in serum potassium, decrease in serum uric acid, and changes in renal function. As is the case with all drugs directly affecting the renin-angiotensin system, Losartan should not be taken by anyone who is pregnant or thinks they may be pregnant. The use of these drugs can cause neonatal injury, hypotension, neonatal skull hypoplasia, anuria, renal failure and death. To our knowledge losartan potassium has not been withdrawn from research or marketing in the United States or any other country.

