#### **Adverse Event Reporting:**

## 8.1 Adverse event definitions

Adverse event means any untoward medical occurrence associated with the use of the drug in humans, whether or not considered drug related.

Adverse reaction means any adverse event caused by a drug.

Suspected adverse reaction means any adverse event for which there is a reasonable possibility that the drug caused the adverse event. Suspected adverse reaction implies a lesser degree of certainty about causality than “adverse reaction”.

- *Reasonable possibility.* For the purpose of IND safety reporting, “reasonable possibility” means there is evidence to suggest a causal relationship between the drug and the adverse event.

Life-threatening, suspected adverse reaction. A suspected adverse reaction is considered “life-threatening” if, in the view of either the Investigator (i.e., the study site principal investigator) or Sponsor, its occurrence places the patient or research subject at immediate risk of death. It does not include a suspected adverse reaction that had it occurred in a more severe form, might have caused death.

Serious, suspected adverse reaction. A suspected adverse reaction is considered “serious” if, in the view of the Investigator (i.e., the study site principal investigator) or Sponsor, it results in any of the following outcomes: death, a life-threatening adverse reaction, inpatient hospitalization or prolongation of existing hospitalization, a persistent or significant incapacity or substantial disruption of the ability to conduct normal life functions, or a congenital anomaly/birth defect.

- Important drug-related medical events that may not result in death, be life-threatening, or require hospitalization may be considered “serious” when, based upon appropriate medical judgment, they may jeopardize the research subject and may require medical or surgical intervention to prevent one of the outcomes listed in this definition. Examples of such medical events include allergic bronchospasm requiring intensive treatment in the emergency room or at home, blood dyscrasias or convulsions that do not result in inpatient hospitalization, or the development of drug dependency or drug abuse.

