#### **8.4 Withdrawal of subjects due to adverse events**

Vital signs, including blood pressure and heart rate will be monitored daily prior to each rehabilitation session. Individuals with symptomatic hypotension (defined as symptoms consistent with hypotension including dizziness, lightheadedness etc. with systolic or diastolic blood pressure less than 90 and 60 mm Hg respectively) will be discontinued from the study. Withdrawal of a subject due to symptomatic hypotension will be reported as an adverse event.

Blood work, including a chemistry panel with electrolytes and complete blood cell count (CBC) will be performed prior to randomization and at 2, 4, and 6 weeks after randomization. The blood work will be used to assess hemoglobin and hematocrit counts, serum potassium and uric acid levels, liver function (alanine aminotransferase (ALT), aspartate aminotransferase (AST) and alkaline phosphatase), renal function (blood urea nitrogen [BUN] and serum creatinine), creatine phosphokinase (CPK) to assess muscle injury, and pregnancy in women (human chorionic gonadotropin (hCG)). Additional blood work will be ordered if subjects report new fatigue, peripheral edema or urinary symptoms. Follow-up blood work will be performed 4-6 weeks ( $\pm 3$  days) after discontinuing medication to ensure that lab values have returned to normal ranges after discontinuation of the study medication. Abnormal lab values resulting in subject withdrawal from the study will be reported as an adverse event.

Human chorionic gonadotropin (hCG) be determined to identify pregnant women will be assessed prior to randomization and at 2, 4 and 6 weeks after randomization. Women that are pregnant prior to randomization will be discontinued from the study, but will not be reported as an adverse event.

Human chorionic gonadotropin will also be determined for females enrolled in the study who expect that they For females enrolled in the study that have become pregnant, the study medication will be stopped immediately and the subject will be withdrawn from the study. Pregnancy necessitating withdrawal from the study will be reported as an adverse event.

Adverse events or abnormal test findings felt to be associated with the study drug(s) will be followed until the event (or its sequelae) or the abnormal test finding resolves or stabilizes at a level acceptable to the Sponsor-Investigator.

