The severity of an adverse event will be determined by the study medical director based on the criteria stated in section 8.1. Additionally, the medical director will assign the event a grade of mild, moderate, or severe. If it becomes medically necessary to withdraw the subject from the study, the study medication will be discontinued. The subject will be followed clinically until the adverse event or abnormal test findings felt to be associated with the study drug resolves or stabilizes at a level acceptable to the Sponsor-Investigator. This follow-up will include assessment of vital signs, physical examination and assessment of blood work. Follow-up blood work will be performed 4-6 weeks ( $\pm 3$  days) after discontinuing medication to ensure that lab values have returned to normal ranges after discontinuation of the study medication. The subject will be treated for any medication related problems as clinically appropriate. Information from this appointment will be documented in the subject's case file. The patient will be terminated from the study, and will not complete any further follow-up appointments for the study. Subjects that are terminated from participation in the study due to an adverse event will be replaced by recruitment of another subject.

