### **13. Study Discontinuation Criteria:**

#### **13.1 Discontinuation of individual research subjects (refer also to sections 5.1.1 and 8.4)**

Because we are interested in evaluating efficacy, we will use a per-protocol approach, as opposed to an intention-to-treat approach for the conduct of this study. As such, subjects that are non-compliant with the medication regimen (defined as taking less than 80% of the medication doses) will be withdrawn from the study and additional subjects will be recruited to replace subjects that have been withdrawn due to non-compliance. Subjects that are withdrawn for non-compliance will be instructed to terminate administration of the study medication without tapering down the dose and to return unused medication to the investigators.

As specified in section 8.4 subjects with symptomatic hypotension or abnormal lab values will be withdrawn from study participation. Additionally, females that become pregnant while taking the study medication will immediately stop the medication and will be withdrawn from the study. These withdrawn subjects will be followed clinically based on standards of care until the adverse event or abnormal test findings felt to be associated with the study drug resolve or stabilize at a level satisfactory to the Sponsor-Investigator, however no further research data will be collected once the subject has been withdrawn.

Subjects that are withdrawn due to non-compliance with the study medication, symptomatic hypotension, abnormal lab values or pregnancy will be reported as an adverse event. Withdrawn subjects will be replaced by recruiting another subject to take the place of the withdrawn subject.

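### The protocol does not plan to record pregnancy or infant outcome after a subject is withdrawn for pregnancy, although it names neonatal harms of the drug class and counts a congenital anomaly as serious

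*Combined protocol and SAP*

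**What the plan says.** Section 1.2 says of drugs acting on the renin-angiotensin system: "The use of these drugs can cause neonatal injury, hypotension, neonatal skull hypoplasia, anuria, renal failure and death". Section 8.1 lists the outcomes that make a suspected reaction serious and ends the list with "or a congenital anomaly/birth defect". Safety and tolerability are Specific Aim 1, and the trial enrols women as well as men, aged 18 to 35.

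Pregnancy is tested before randomization and at weeks 2, 4 and 6 (3.1, 7.2, 8.4), with dosing for four weeks.

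For a subject who has become pregnant, 8.4 says "the study medication will be stopped immediately and the subject will be withdrawn from the study". Section 13.1 says the same of those who conceive on treatment: "females that become pregnant while taking the study medication will immediately stop the medication and will be withdrawn from the study". The event itself is recorded: "Pregnancy necessitating withdrawal from the study will be reported as an adverse event".

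After withdrawal, two provisions apply:

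- Section 13.1 keeps withdrawn subjects "followed clinically based on standards of care until the adverse event or abnormal test findings felt to be associated with the study drug" have cleared or settled, and closes the same sentence with "however no further research data will be collected once the subject has been withdrawn".
- Section 8.4, on medically necessary withdrawal, describes follow-up by vital signs, physical examination and blood work, entered in the case file, with laboratory tests repeated 4-6 weeks after stopping. It then says: "The patient will be terminated from the study, and will not complete any further follow-up appointments for the study".

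Under 8.2.1, subjects are asked about adverse events at study visits and follow-up calls.

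**The concern.** The protocol tests for pregnancy and records that it occurred, but it plans no step to learn how the pregnancy ended or how the infant fared. The neonatal harms in 1.2 and the congenital-anomaly criterion in 8.1 can be assessed only at or after the end of the pregnancy. By then the subject has left the study and is outside the contacts at which adverse events are asked about. For a trial whose first aim is safety, the gravest harm it names would have a detection test but no planned outcome.

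**Working it through.** The plan gives no figure on this point to reproduce. The check has two parts: what follow-up survives withdrawal, and whether the outcome would fall within the study's planned duration.

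**What survives withdrawal**

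| Source | Provision | Reaches pregnancy or infant outcome? |
|---|---|---|
| 8.2.1 | Adverse events elicited at visits and calls | No; withdrawal removes these |
| 8.2.2 | Drug-associated events followed, including sequelae, until resolved or stable | Only if the pregnancy is judged drug-associated |
| 8.4 | Vital signs, examination, blood work; entered in the case file | Not as stated; the content is maternal |
| 13.1 | Clinical follow-up under standard care; no further research data | No stated end at delivery; infant not mentioned |
| 8.3 | Reports on events observed or volunteered | Only if someone happens to report the outcome |

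No row sets out a planned step that obtains the outcome.

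**Timing**

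Inputs from the documents:

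- dosing in weeks 0-4 (3.1);
- scheduled pregnancy tests at weeks 2, 4 and 6 (3.1);
- follow-up blood work 4-6 weeks after stopping (8.4);
- follow-up to 12 months after injury (3), with dosing begun within 7 days of injury (5).

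Input assumed, because the documents do not give it: 38 weeks from conception to delivery, range 35-40.

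1. Last stated clinical contact, ignoring the ±3 days. Stopping at the week 2 test gives 2 + 4 to 2 + 6 = weeks 6-8. Stopping at the week 4 test gives 4 + 4 to 4 + 6 = weeks 8-10. Overall: weeks 6-10.
2. Delivery, central assumption: 0 + 38 to 4 + 38 = weeks 38-42.
3. Delivery, full range: 0 + 35 to 4 + 40 = weeks 35-44.
4. Shortest gap between steps 1 and 3: 35 − 10 = 25 weeks, about six months with no stated contact.
5. 12-month contact: 52 weeks after injury, less up to 1 week before dosing, gives weeks 51-52 after randomization.
6. Latest delivery against the 12-month contact: 44 is less than 51.

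Delivery would usually come before the last scheduled contact. The study is long enough to learn the outcome, and the withdrawal rule is what removes the opportunity.

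**The week 6 test**

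This test comes 6 − 4 = 2 weeks after dosing ends. Section 13.1 addresses pregnancy arising while the medication is being taken, and 8.4 speaks of stopping a medication that has already finished. Neither fits a pregnancy first found at week 6. Even with conception taken as late as week 6, delivery falls no later than 6 + 40 = week 46, still before week 51.

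**The case against.** The strongest reply is that follow-up does not simply stop. The first half of the 13.1 sentence keeps withdrawn subjects under clinical follow-up. The condition about association with the drug may attach only to test findings and not to the adverse event. Since pregnancy is itself a reported adverse event, follow-up until it resolves could be read to run to delivery. Section 8.2.2 extends to sequelae, 8.4 requires case-file entries, and 8.3 sets no cut-off at withdrawal.

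Much of this stands. A reader might infer that all data collection ends and that these harms can never be captured. The documents do not support that: an anomaly that is volunteered or seen in clinical care could still be recorded and assessed. The wider reading of 13.1 is also possible. It does not supply a plan, however. It depends on how an ambiguous clause is taken, the stated assessments remain maternal, and the same sentence rules out further research data.

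A reader might also infer that FDA and IRB reports would be lost. That is largely unsupported. Reports under 8.3 require an unexpected event, and 8.1 defines unexpected as not listed in the protocol, or not at the observed specificity or severity. Section 1.2 lists most of the harms at issue, so many would not qualify for expedited reporting even with complete data.

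Finally, a sentence on additional pregnancy testing in 8.4 is broken off, and the consent pages, case report form and operations manual are not visible. The finding is limited to the text available.

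**Conclusion.** The concern holds in limited form. On the visible text there is no planned capture of pregnancy or infant outcome after withdrawal. Capture would depend on a volunteered report or on clinical follow-up whose end and content are not specified for this purpose. The loss of appointments comes from 8.4 and the loss of research data from 13.1. Applying the 8.4 wording to pregnancy assumes that such a withdrawal counts as medically necessary; the 13.1 wording covers pregnancy expressly.

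The scale is small. There are 20 subjects, 10 per group, only some of them women, with four weeks of dosing. The documents give neither a sex split nor a pregnancy rate, so no expected count can be calculated. No effectiveness endpoint is affected. The change is still worth making, because it concerns the most severe harm the protocol names and costs little. The timing argument rests on the assumed 35-40 weeks to delivery and holds across that range.

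The point does not depend on length of exposure. A reader might infer more than two weeks' exposure if conception just preceded the baseline test. Dosing starts only at Day 0, so a pregnancy missed at baseline and found at week 2 has about two weeks of exposure; more would need a second missed test.

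**What to change.** - In 8.4 and 13.1, exempt pregnancy outcome and infant status from the rule that ends research data collection. With the subject's consent, record them through the later contacts already scheduled, up to the 12-month call, until the outcome is known.
- State that this also covers a pregnancy first detected at the week 6 test.
- Assess any resulting event for seriousness under 8.1, and report it under 8.3 only where it also meets the unexpected and suspected criteria.
- Reconcile 8.2.2, 8.4 and 13.1 on what safety information is recorded after withdrawal, for how long, and whether association with the drug is a condition for following the event or only for following test findings.

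None of this alters dosing, the withdrawal rule or clinical care. The cost is protocol and consent wording and one outcome form. The 6-month contact is a visit, not a call, and 8.2.1 schedules a clinic visit when a new or ongoing adverse event is reported by telephone, so an occasional extra visit is possible.

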### **5.1.1 Withdrawal of subjects due to non-compliance/adherence**

Because we are interested in evaluating efficacy, we will use a per-protocol approach, as opposed to an intention-to-treat approach for the conduct of this study. As such, subjects that are non-compliant with the medication regimen (defined as taking less than 80% of the medication doses) will be withdrawn from the study and additional subjects will be recruited to replace subjects that have been withdrawn due to non-compliance. Subjects that are withdrawn for non-compliance will be instructed to terminate administration of the study medication without tapering down the dose and to return unused medication to the investigators.

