## 9.

## **Statistical Methods/Data Analysis:**

### **9.1 Study endpoints**

#### **9.1.1 Primary endpoint(s)**

**Specific Aim #1: To determine safety and tolerability of Losartan when used for treatment of an acute grade II or III hamstring strain.**

To assess safety, vital signs will be monitored daily and we will also monitor the frequency of abnormal lab values as well as adverse and serious adverse events during period of active intervention as well as throughout the subjects' participation in the study. To assess the side effect profile of Losartan in this population, we will monitor the frequency of subject complaints, symptoms (dizziness, new fatigue, peripheral edema, urinary symptoms) and laboratory measures of liver and renal function, haemoglobin and haematocrit counts and serum potassium and uric acid levels. The frequency of abnormal lab values, adverse and serious adverse events and side effects will be monitored separately for the Losartan and placebo control groups.

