## **9.5 Safety analysis**

To assess safety, vital signs will be monitored daily and we will also monitor the frequency abnormal lab values as well as adverse and serious adverse events during period of active intervention as well as throughout the subjects' participation in the study. To assess the side effect profile of Losartan in this population, we will monitor the frequency of subject complaints, symptoms (dizziness, new fatigue, peripheral edema, urinary symptoms) and laboratory measures of liver and renal function, hemoglobin and hematocrit counts and serum potassium and uric acid levels. The frequency of abnormal lab values, adverse and serious adverse events and side effects will be monitored separately for the Losartan and placebo control groups. Differences between groups will be assessed using Fisher exact tests.

Any deviations from the previously described statistical plan will be described and justified in a protocol amendment and/or in the final report submitted to the IND application.

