#### **13.2 Sponsor-Investigator discontinuation of the clinical research study**

Adverse events will be continuously monitored by the Data and Safety Monitoring Committee. If the number or severity adverse events are greater than the expected adverse events associated with Losartan, the DSMC will make the recommendation for termination or modification of study.

Any modifications in the study protocol will be submitted for review and approval by the IRB before the modification is implemented. Modifications in the study protocol will be communicated to all study sites in writing. Subjects will be notified of modifications in the study protocol and if appropriate will be re-consented for their continued participation in the modified study.

If the DSMC recommends termination of the study due to safety concerns, the IRB and all study sites will be notified immediately by the study principal investigator, followed by notification in writing. Enrolled subjects will be notified of the study termination by the site principal investigator by phone, and also in writing. If subjects are taking study medication at the time of study termination, they will be instructed to discontinue the study medication as clinically appropriate.

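### Section 13.1 reports withdrawal for missed doses as an adverse event, which does not fit the definition in 8.1 and puts adherence failures into the primary safety counts

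*Combined protocol and SAP*

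**What the plan says.** Section 13.1 withdraws subjects for non-compliance, "defined as taking less than 80% of the medication doses", and then says that subjects "withdrawn due to non-compliance with the study medication, symptomatic hypotension, abnormal lab values or pregnancy will be reported as an adverse event". Its heading refers the reader to 5.1.1 and 8.4.

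- **Section 8.1** gives the definition: "Adverse event means any untoward medical occurrence associated with the use of the drug in humans, whether or not considered drug related".
- **Section 5.1.1** has the same 80% rule and the same replacement rule ("additional subjects will be recruited to replace subjects that have been withdrawn due to non-compliance") but does not mention adverse-event reporting.
- **Section 8.4**, on withdrawal because of adverse events, covers symptomatic hypotension, laboratory values ("Abnormal lab values resulting in subject withdrawal from the study will be reported as an adverse event") and pregnancy. It does not mention non-compliance.

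Adverse-event counts are then used in three places:

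- **Section 9.1.1, Aim 1 primary endpoint:** "The frequency of abnormal lab values, adverse and serious adverse events and side effects will be monitored separately" for the two arms.
- **Section 9.5:** "Differences between groups will be assessed using Fisher exact tests".
- **Section 13.2:** "If the number or severity adverse events are greater than the expected adverse events associated with Losartan", the Data and Safety Monitoring Committee is to recommend stopping or modifying the study.

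**The concern.** A low pill count is not in itself a medical occurrence. A subject who forgets or declines tablets and is otherwise well has had no adverse event under 8.1, yet 13.1 requires one to be reported. The two sites could therefore record different adverse-event counts from identical subjects, depending on which section they follow.

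Safety and tolerability is the first aim, and Hypothesis 1a is that the adverse-event profile on losartan is acceptable and comparable to placebo. With 10 subjects per arm, a few reports unrelated to health can change how that profile reads. If they fall mainly in one arm they can suggest or hide a difference. If they fall equally in both they dilute a real one. The comparison in 13.2 is also mismatched, because the events expected with losartan would not include missed tablets.

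**Working it through.** The plan states no figure that depends on this rule, so there is nothing to reproduce. The check has two parts.

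**1. Do the reports reach the counts?**

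- Section 13.1 makes the withdrawal an adverse event on pill count alone. Four weeks of once-daily dosing is 28 doses, and 0.80 × 28 = 22.4, so 22 or fewer doses taken is non-compliance. No symptom or finding is needed.
- Section 8.1 requires a medical occurrence but does not require a causal link to the drug.
- Section 8.2.2.2 has the Sponsor-Investigator judge causality for each event, but no text removes an unrelated event from a count.
- Sections 9.1.1, 9.5 and 13.2 use adverse events without limiting them to drug-related ones.

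A report made under 13.1 therefore stays in all three uses.

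**2. How large is the effect?**

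From the documents: 20 subjects, 10 per arm (9.2), and replacement of withdrawn subjects (5.1.1, 13.1). Assumed, because the documents give no values: non-compliance q of 5%, 10% or 20%; true proportion of subjects with an adverse event p = 20%; independence of the two; two-sided 5% level for Fisher's test.

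*Chance of at least one such report among 20 subjects*, 1 − (1 − q)^20:

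- q = 5%: 1 − 0.95^20 = 0.64
- q = 10%: 1 − 0.90^20 = 0.88
- q = 20%: 1 − 0.80^20 = 0.99

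Replacement subjects can only raise these figures.

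*Expected number of subjects with an event*, 20 × [1 − (1 − p)(1 − q)] with p = 0.20. Without the rule it is 4.0 of 20.

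- q = 5%: 20 × (1 − 0.80 × 0.95) = 4.8
- q = 10%: 20 × (1 − 0.80 × 0.90) = 5.6
- q = 20%: 20 × (1 − 0.80 × 0.80) = 7.2

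*One non-complier with no other event, in an arm that would otherwise read 2/10 = 20%:*

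- all exposed subjects counted, with an event-free replacement: 3/11 = 27.3%, a rise of about 7 points
- denominator held at 10: 3/10 = 30%, a rise of 10 points

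*Fisher's test, two-sided:*

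| Comparison | p |
|---|---|
| 4/10 v 0/10 | 0.087 |
| 5/10 v 0/10 | 0.033 |
| 5/11 v 0/10 (fifth event from a replaced non-complier) | 0.035 |
| 5/10 v 2/10 | 0.35 |
| 7/10 v 2/10 | 0.070 |
| 8/10 v 2/10 | 0.023 |
| 8/16 v 2/10 (six non-compliers replaced) | 0.22 |

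One report can cross 0.05 from 4 v 0. From 2 v 2 with 10 per arm, six extra reports in one arm and none in the other are needed. With event-free replacements even six do not reach 0.05.

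*Direction, with the denominator fixed at 10 per arm (replacement ignored):*

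- Equal non-compliance in both arms, true rates 50% v 10%: power falls from 29.5% to 20.0% at q = 10% and 14.3% at q = 20%.
- Non-compliance on losartan only, true rate 20% in both arms: the chance of a significant difference rises from 0.8% to 1.6% at q = 10% and 4.0% at q = 20%.

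**The case against.** The strongest reply is that this is a wording slip with little effect on any conclusion. Several parts of that reply stand.

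- **Attribution.** A reader might infer that missed tablets are counted as harm caused by losartan. The documents do not say so. Section 8.1 counts events whatever their cause, and 8.2.2.2 judges causality separately. The reports enter the counts used to judge safety, but they are not declared drug-related.
- **Size.** A reader might infer that every non-complier adds 10 percentage points. That holds only if the denominator stays at 10 and the subject had no other event. Replacement lowers the step, and a non-complier who already had an adverse event does not change a per-subject rate.
- **Stopping.** A reader might infer that these reports could trip the rule in 13.2. That section has no numeric threshold. The committee weighs number or severity and makes a recommendation, and its members, who include the site principal investigators and the statistician, could recognise a report of missed tablets.
- **Section 8.4.** It might look like a direct contradiction of 13.1. It deals with withdrawal because of adverse events, so its silence on non-compliance is not a conflict. The conflict is between 13.1 and 8.1.
- **Form of analysis.** Sections 9.1.1 and 9.5 do not say that one pooled any-event proportion is tested. If events were tabulated by type, non-compliance would show as its own row.

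It can also be said that non-compliance may signal intolerance. If a symptom led to the missed doses, that symptom is already an adverse event under 8.1 and is asked about under 8.2.1. Reporting the withdrawal as well counts one problem twice and does not record the reason.

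The core is untouched. The rule in 13.1 does not fit the definition in 8.1, and nothing takes these reports out of the counts. Section 9.2 says that the trial lacks power for clinical differences, so the descriptive frequencies carry the safety message, and those are the figures affected.

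**Conclusion.** The point holds as an internal inconsistency that miscounts the primary safety endpoint if 13.1 is followed. It should be corrected.

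Withdrawals defined by pill count alone enter the Aim 1 frequencies, the Fisher comparison and the committee's comparison with expected losartan events. The bias has no fixed direction.

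The size rests on a non-compliance rate that the documents do not give. Over an assumed 5% to 20%, with subjects independent, at least one such report is likely (64% to 99%). Each event-free case shifts an arm by about 7 to 10 points from a base of 2/10, depending on the denominator. These figures show that contamination is probable. They do not show that a test result or a committee decision would change, which usually needs several such cases in one arm.

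**What to change.** 1. In 13.1, delete the reference to non-compliance from the sentence on adverse-event reporting, so that it agrees with 8.1 and 5.1.1.
2. State that where a medical event lies behind the missed doses, that event is the one reported under 8.1.
3. State in 9.1.1, 9.5 and 13.2 that non-compliance withdrawals are tabulated by arm as a separate disposition item and are not counted as adverse events.
4. In 9.5, state the safety denominator, in particular whether withdrawn subjects and their replacements are both counted.

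The cost is a few sentences and one new data field. Pill counts measure adherence, and the log records when study and concomitant medications were taken (5.1). The reasons sought in 5.5 are for concomitant medications. Neither source records why study doses were missed, so a reason field is needed at the existing weekly log review. No extra visit or test is needed.
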